Official Title: Evaluation of Motor Unit Abnormalities after Experimentally Induced Sensitization Using Capsaicin: A Randomized, Double-Blinded, Placebo-Controlled Study

NCT Number: Not Assigned

Date of Document: October 1st, 2019

Abstract

Central sensitization is a condition that represents a cascade of neurological adaptations, resulting in an amplification of nociceptive responses from noxious and non-noxious stimuli. However, whether this abnormality translates into motor output and more specifically, ventral horn abnormalities, needs to be further explored. Twenty healthy participants aged 20-70 will be randomly allocated to topical capsaicin or a placebo topical cream which will be applied onto their left upper back to induce a transient state of sensitization. Visual analogue scale (VAS) ratings of pain intensity and brush allodynia score (BAS) will be used to determine the presence of pain and secondary allodynia. Surface electromyography (sEMG) and intramuscular electromyography(iEMG) will be used to record motor unit activity from the upper trapezius and infraspinatus muscles before and twenty minutes after application of capsaicin/placebo. Motor unit recruitment and variability will be analyzed in the sEMG and iEMG, respectively. An independent t-test will be performed on the data. This preclinical evidence may provide some explanation for the influence of central sensitization on changes in movement patterns that occur in patients who have pain encouraging of further clinical investigation.

Keywords: Central Sensitization; Surface Electromyography; Intramuscular Electromyography; Motor Unit; Recruitment

1. Introduction

Chronic pain is characterized by pain lasting longer than three months [1-3]. It is a common condition affecting 1 in 5 people [4] and is rising due to the aging population and increased prevalence of comorbid conditions such as diabetes [5,6] and obesity [7]. Chronic pain produces

a significant socioeconomical burden with the annual estimated cost in Canada exceeding 6 billion dollars [4,8-11]. As such, the assessment and diagnostic efficacy of chronic pain is of vital importance to improving its management throughout society.

Central sensitization describes a state of neuronal hyper-excitability in the central nervous system that may occur due to malfunction of spinal and supraspinal pain facilitatory and inhibitory circuits resulting in amplification of somatosensorial responses [12]. Beyond somatosensorial changes, alteration in motor function can also be present with pain, and may be a reflex of neuromuscular function impairment [13,14]. A normal afferent input and normal central processing circuitry is essential to deliver normal efferent output. However, the influence of the changes that occur within the dorsal horn on the ventral horn remain largely ill defined [15,13].

Motor unit assessment is crucial in evaluating diseases and abnormalities within the ventral horn [16]. Activity of the ventral horn, where anterior horn cells reside, is very important for motor unit activation [16]. Surface EMG (sEMG) [17] and intramuscular EMG (iEMG) [18] can be used to assess the neural drive to muscles, by recording motor units to understand the effects of central sensitization on motor control and the ventral horn. Based on Henneman's size principle, motor units should be recruited in the same order, with smaller units being recruited first [19]. This principle presents an opportunity to investigate if central sensitization creates abnormalities on the motor unit level.

Previously, central sensitization has been induced in healthy subjects to examine its neurophysiological effects via capsaicin [20-22]. Capsaicin, a chilli pepper extract, can be used to effectively induce experimental transient states of central sensitization. [23-25,21,22]. The presence of expanded sensorial responses and the involvement of the spinal nociceptive system

post capsaicin have been largely tested by means of quantitative sensory testing methods and electromyography (EMG) [25,21,22,24].

Despite the usefulness of experimental capsaicin to better understand the sensorial abnormalities, its impact on motor function and motor unit recruitment are lesser studied. Evidence suggests that nociceptive input by peripheral capsaicin exerts a centrally-mediated inhibitory effect on motor function [26]. A decrease in root mean squared (RMS) amplitude during exercise at the time of peak sensitization was measured by needle EMG [26]. However, the effect that capsaicin-induced sensitization has on individual motor units or on their recruitment patterns has not been previously examined.

The purpose of this study is to determine whether topical capsaicin-induced sensitization has any influence on ventral horn activity. We hypothesize that capsaicin induces a change in individual motor unit activity, as well as the recruitment pattern of many motor units, and may affect motor unit activity at different segmental levels from the level of capsaicin application.

2.2 Dataset Collection

An initial screening will be performed to assess eligibility in the study. Each participant will be seated upright with their hands comfortably on their lap and asked to relax their neck and shoulder muscles. The physician member of the research team will then assess the patients' pain intensity by visual analogue scale (VAS). VAS ranges from 0 to 100 mm which 0 mm reflecting no pain at all and 100 mm representing the worst imaginable pain [29]. Following this, brush allodynia, a clinical technique used to identify pain due to a stimulus that does not normally provoke pain, will be performed to confirm presence of central sensitization [12]. To map out borders of secondary allodynia, subjects will be instructed to recognize a distinct alteration in the sensation perception such as increased burning, intense pricking, or an unpleasant sensation, and that location will be marked [31]. Brush allodynia score (BAS) will be calculated as the distance between the farthest points marked on the superior and inferior axis multiplied by the distance between the farthest points marked on the medial and lateral axis as previously described by Cavallone et. al. [31]. The VAS and the presence of central sensitization by means of BAS will be assessed at baseline (pre) before the induction of sensitization and twenty minutes after (post).

Upon successful screening of inclusion and exclusion criteria, participants will have their left side area of skin (overlying the upper trapezius and infraspinatus muscles) cleansed with alcohol preparation pads and water. The skin will be abraded with '3M Red Dot' abrasive strips before application of the surface electromyogram (Trigno Galileo sensors, *Delsys Inc.*). Electrodes will be placed in 4 areas: the muscle belly of the upper trapezius, and the infraspinatus, as well as reference electrodes on C7 and the acromion. These electrodes are 4 channel EMG sensors and have their signals filtered from 20 – 450 Hz. The sEMG recordings are wirelessly transmitted to the Trigno base station, which relays and compiles the data to Neuromap (*Delsys Inc.*) for signal analysis. A monopolar needle electrode will be inserted into the upper fibers of trapezius muscle and its reference will be placed at the mid-clavicle point. Using this setup intramuscular recordings of single motor units will be performed using an Excaliber, *Natus Medical* clinical electrodiagnostic machine.

2.2.1 Electromyograms recordings before application of intervention

Participants will then be instructed to perform horizontal shoulder abductions from 0° to 90° and then from 90° to 0° for 1 minute. The study subject will be verbally cued to move their arm every 2 seconds. sEMGs were recorded during this time. Upon completion of this task, a monopolar intramuscular needle electrode will be placed directly into the upper trapezius muscle. Participants will then be instructed to gently contract their trapezius muscle by shrugging their shoulder, enough to recruit only the first motor unit in that region. Visual feedback of the signal will be given to the subject to ensure that only the first motor unit was activated for the movement. iEMG recordings will be recorded for 30 seconds at a sampling frequency of 6 kHz.

2.2.2 Application of intervention

Participants will receive either a dose of 2.5 ml (75 μ g/ml) capsaicin cream (treatment, Zostrix brand) or skin lotion (placebo) which is inert and causes no sensitization effects. Participants will also be blinded to the delivered treatment, using concealed containers for the creams. The location of application will be a 10 cm by 10 cm square on trapezius muscle which extends from T3 to T8 on the left side that all recordings were conducted.

After collection of the baseline sEMG and iEMG recordings, a trained medical professional will apply the capsaicin / placebo cream directly to the region of skin in a standardized 10 cm x 10 cm square at the spinal levels T3-T8, to sensitize the nociceptive afferents within that region. A twenty-minute waiting period will be used to enable the sensitizing effects of capsaicin to take effect.

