2.2.3 Electromyograms recordings after application of intervention

To confirm the presence of central sensitization, brush allodynia will be used to detect mechanical allodynia outside the region of the primary nociception – region of topical placement – which is the region of secondary allodynia [25]. Upon confirmation of central sensitization, in participants with application of topical capsaicin, participants will be entered into the experimental arm of the study.

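### The title says double-blinded, but a blinding procedure is described for participants only, and the capsaicin-specific entry rule in 2.2.3 is hard to reconcile with blinded staff

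*Combined protocol and SAP*

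**What the plan says.** The title describes the study as "A Randomized, Double-Blinded, Placebo-Controlled Study". Outside the title, section 2.2.2 is the only place that says how anyone is blinded: "Participants will also be blinded to the delivered treatment, using concealed containers for the creams". The same section says that "a trained medical professional will apply the capsaicin / placebo cream directly to the region of skin", without saying whether that person knows which cream it is. It describes the comparator as "skin lotion (placebo) which is inert and causes no sensitization effects".

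Section 2.2.3 carries the heading for the post-intervention EMG recordings. It starts with the brush allodynia check and then states: "Upon confirmation of central sensitization, in participants with application of topical capsaicin, participants will be entered into the experimental arm of the study". It names nobody as responsible for this step and does not describe the post-treatment recording itself.

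On timing, section 2.2 places the VAS and brush allodynia assessments at baseline and twenty minutes after application. The abstract places the second EMG recording at the same twenty minutes.

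On how recordings are obtained, section 2.2.1 (the baseline procedure) has the participant cued verbally every 2 seconds during the surface EMG task. A needle is then inserted by hand and the participant is told to shrug gently. The feedback goes to the participant: "Visual feedback of the signal will be given to the subject to ensure that only the first motor unit was activated".

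**The concern.** Double-blinded tells a reader that staff who can influence the outcome do not know the allocation. Here the text supports that for participants only, and one rule appears to run against it for staff.

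If the person who obtains the post-treatment recordings knows or can infer the arm, that knowledge can affect how the needle is placed, how the contraction is coached and how firmly effort is encouraged. The trial is small (twenty participants in the abstract, twenty-three in section 2.1, nine per group in section 3), so a few recordings handled differently could matter. If the analyst knows the arm, the decision about which participants have an acceptable match is exposed too. A reader would credit the result with protection that the written procedure does not secure.

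**Working it through.** The point contains no figure of its own, so the check is a reading of the passages against each other.

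**1. Parties who would need to be blinded, and what the documents provide.**

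| Party | Blinding procedure described | Place |
|---|---|---|
| Participant | Yes, concealed containers | 2.2.2 |
| Person applying the cream | None | 2.2.2 |
| Allodynia assessor | None | 2.2, 2.2.3 |
| EMG operator | None | 2.2.1, 2.2.3 |
| Analyst | None | 2.3, 2.4 |

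No coded containers, unblinded third party or code-break step is described.

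**2. Does 2.2.3 need the allocation?** The rule has two conditions: confirmed sensitization and receipt of capsaicin. The second cannot be evaluated without the allocation. As written, the rule therefore requires someone to know it.

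**3. When?** The documents give no explicit order. Two facts point to the post-treatment session: the rule sits under the heading for the post-intervention EMG, and the allodynia check and the second EMG share the twenty-minute time point. This is an inference.

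**4. Can the arm be inferred without disclosure?** The lotion is said to cause no sensitization, so a mapped area of secondary allodynia is itself a strong clue to capsaicin. Nothing separates the person who maps it from the person who records the EMG.

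**5. Where could knowledge of the arm act?** This assumes that the post-treatment recording repeats the baseline procedure, which the documents imply but do not state.

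- *Intramuscular EMG:* needle placement and the coached gentle contraction are manual. Under 2.3.2, participants whose best match is below 0.95 are left out of the statistical analysis, so the way the post recording is obtained can affect who is analysed. Under 2.4.2, the choice of test also depends on how many participants match.
- *Surface EMG:* section 2.2 places the sensors before treatment, and 2.3.1 leaves decomposition, recruitment order and matching to software with preset thresholds. What remains is verbal cueing and encouragement of effort.
- *Brush allodynia score:* the participant reports a change in sensation and the assessor marks it, so the measure that gates entry is itself subjective.

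**6. Does the sample size calculation bear on this?** With a difference of 5, SD 3, two-sided 5% (sidedness is not stated) and 80% power, the t-test requirement is 6.76, rounded up to 7 per group (power 81.6%). With 20% dropout, 7 / (1 − 0.20) = 8.75, rounded up to 9. The plan's 7 and 9 reproduce. Bias from unblinded recording is not an input to that calculation, so these figures neither show nor rule it out.

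**The case against.** Section 2.2.3 names no actor and no order. Entry into the experimental arm could mean classification for analysis, made by someone who never records EMG, or made after the code is broken. In 2.2.2 the word also may hint that another party is blinded, and concealed containers could mask the applier as well. Matching is automated. On this view the plan has a reporting gap and nothing more.

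Much of this stands. A reader might infer that staff must know the arm before the post-treatment EMG and that double-blinding therefore fails. The documents do not support that: a separate unblinded person is possible, though none is described. A reader might also take the first-motor-unit check in 2.2.1 as a staff judgement, but the text gives that feedback to the participant.

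A reader might also try to put a number on the harm. With SD 3, 10 per arm and a two-sided t-test, an artificial shift of 1 position in mean recruitment change would raise the false-positive rate from 5% to 10.9%, and a shift of 2 to 29.2%. At 9 per arm the figures are 10.2% and 26.5%. The arithmetic is right, but nothing in the documents supports either shift. The SD also belongs to the surface EMG outcome, where staff influence is narrowest. No SD is given for the intramuscular outcome. The direction of any bias is equally unknown, because the hypothesis is only that a change occurs.

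What the objection does not remove is the conflict itself. A hint in one adverb is not a procedure, automation acts only after the signal has been acquired, and the rule in 2.2.3 cannot be applied blind as it is written.

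**Conclusion.** The point holds in limited form. The title states a property for which the plan gives a procedure on the participant side only, and 2.2.3 contains an allocation-dependent rule that sits badly with the other side. This goes beyond missing detail, because a stated rule conflicts with a stated property. It falls short of showing that staff were or will be unblinded.

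The conclusion rests on two readings: that the post-treatment session is where the 2.2.3 rule is applied, and that the post recording follows the baseline procedure. The exposure is mainly in the intramuscular EMG and is smaller in the surface EMG. Its size cannot be estimated from the documents, and no figure should be attached to it. The change should be made because it is cheap and settles whether the label is true.

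**What to change.** - Delete the arm-specific entry condition in 2.2.3. Do the allodynia check identically in both arms and analyse all participants as randomized.
- State who is blinded among the applier, allodynia assessor, EMG operator and analyst. Use coded containers, prepared by someone not involved in assessment.
- Have existing staff map allodynia without knowing the allocation, and keep the result from the EMG operator.
- Store recordings under coded IDs. Lock unit matching, exclusions and per-person averages before the code is broken.
- If this cannot be done, describe the design as participant-blinded in the title and conclusion.

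Two tempting measures are best left out. Having the person who applies the cream also map allodynia would protect the EMG by exposing the subjective allodynia score. Asking for allocation guesses would say little, because capsaicin is meant to be felt and the lotion is inert, so a correct guess does not distinguish failed concealment from the intended effect.

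The cost is role assignment among existing staff, file coding and protocol wording. The downside is minor logistics on the day or, on the alternative route, a less favourable blinding label.

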2.2.3 Electromyograms recordings after application of intervention

To confirm the presence of central sensitization, brush allodynia will be used to detect mechanical allodynia outside the region of the primary nociception – region of topical placement – which is the region of secondary allodynia [25]. Upon confirmation of central sensitization, in participants with application of topical capsaicin, participants will be entered into the experimental arm of the study.

2.3 Study Procedures for EMG Analyses

This section outlines the procedures for the EMG analysis. For the sEMG data, the pre-recording motor units will be matched with an algorithm implemented in MATLAB (Mathworks, version 2018a), described in section 2.3.1, in order to determine the aberration of recruitment pattern after treatment.

For the iEMG data, the pre- and post-recording motor units will also be matched using an algorithm implemented in MATLAB (Mathworks, version 2018a), described in 2.3.2. The variability of that motor unit shape will be compared before and after capsaicin and between groups.

2.3.1 *Surface EMG*

Recorded sEMGs will be analyzed in *Neuromap* [32], which provides an average template, average amplitude, and order of recruitment of each motor unit detected and isolated from the raw signal using *Delsys*' motor unit decomposition algorithm [33]. Each motor unit template will then be analyzed based on their “overall match” in shape and amplitude.

Shape Analysis

The motor unit signal that will be obtained from M electrode contacts at T consecutive time samples will be assembled into an $M \times T$ matrix. This matrix will then be compressed into a single vector to create a motor unit “signature” [34]. This will be done by taking the recordings from all electrode contacts at a single time step and concatenating it to the recordings from all contacts at the next time point. This concatenation will be repeated to the time T to create the signature (**Figure 1**). This process will be performed for the pre- and post-recording motor units for each participant.

The shape of each detected pre-recording motor unit will be compared to the shape of each post-recording motor unit via the cross-correlation function, *xcorr*, in *Matlab* (Mathworks, 2018a). This function returns a normalized value between 0 – 1 between each pre- and post-recording motor unit. Cross-correlation values between pre- and post-recording motor unit pairs that are

below a preset threshold of 0.8 [35] will be set to 0 as the pair is unlikely to be from the same motor unit.

Amplitude Analysis

The motor unit average amplitudes obtained from the *Neuromap* software will be used for calculating an amplitude ratio between pre- and post-recording motor units. This amplitude ratio will be calculated for each pre/post motor unit pair to determine similarities in the amplitude. Similar to the shape analysis, amplitude ratios that are below a preset threshold of 0.8 or above 1.2 are set to 0. This ratio will be normalized to be within a scale from 0 – 1 to allow for comparison between shape and amplitude using the following equation (Eq.1) when the amplitude ratio is above one.

$$\text{Normalized Amp. Ratio} = 1 - \text{Amp. Ratio} \quad (1)$$

The numbers from the shape analysis and amplitude analysis, which are not set to 0, will be averaged together to express an “overall match” between pre- and post- motor units from each participant. As mentioned, based on Henneman’s size principle, motor units should be recruited in the same order with smaller units being recruited first and subsequent motor units are recruited as more force is needed [19]. To observe whether this principle is upheld or violated, the reorganization of the recruitment will be identified by how much earlier or later the similar motor units were recruited. In order to quantify the recruitment, the difference in the order of recruitment between the pre and post recording will be calculated. Recruitment order of motor units will be

determined through a custom automated search algorithm (Algorithm 1), which will determine the best match between pre- and post-recording motor units.

Algorithm 1: Automated Motor Unit Matching method

Input: Matrix of averaged values from shape and amplitude analysis

Output: Matched pre-post motor units

- 1: **loop** through each pre-motor unit (row) and each post-motor unit (col)
- 2: **if** value at current location is the highest in that row and column, **and** the number is not equal to zero
- 3: **Record** match between the pre- and post- motor unit, and set the row and col to 0 (i.e. remove the pre- and post- motor unit from further pairing)
- 4: Return matched pre-post motor unit pairs

The average recruitment order difference for each motor unit will be obtained for each participant. Following this, for each participant, the recruitment difference for all of their motor units will be averaged, to obtain one vector of average recruitment changes per person. This final matrix containing numbers on a continuous scale, will be used for statistical testing. See Appendix A for a detailed explanation of the matrix set up.

2.3.2 *Intramuscular EMG analysis using template matching*

Recorded iEMGs will be thresholded using the median absolute deviation estimate approach (**Eq.2**) to find the peak location of motor unit action potentials (MUAPs) [36].

$$Threshold = 10 \times \frac{Median(|X|)}{0.6745} \quad (2)$$

Each detected peak, along with 12.5 ms before and after will be stored and used for analyses. These detected MUAPs will then be clustered to determine the number of motor units present in the recording. In particular, the first detected peak and its surrounding environment (i.e. the MUAP) forms the first motor unit template. Subsequent detected MUAPs will be compared to the first template using cross correlation. If the cross correlation is more than 0.85, it will be determined as the same MUAP and added to that motor unit cluster and the template will be updated. However, if the cross-correlation is less than 0.85, it will be classified as a different motor unit and a new template cluster will be created for comparison.

This process will be repeated until all of the detected MUAPs in the pre- and post-recording are classified. The MUAP cluster with the highest number of MUAPs, for the pre-recording, will be compared with all MUAP clusters found in the post-recording for each participant. The MUAP cluster in the post that has the highest cross-correlation value will be considered “matched.” Participants that do not have matched MUAPs with cross-correlation values above or equal to 0.95 will not be used for statistical analysis.

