2.4 Statistical Methods

2.4.1 Surface EMG

An independent samples t-test will be performed on the difference in recruitment position using treatment as the factor for the trapezius muscle. In particular, the statistical test will compare

post-pre capsaicin recruitment differences against post-pre placebo recruitment differences. The average difference in recruitment order will be used to avoid bias of having multiple data points per participant that correspond to different motor units.

2.4.2 *Intramuscular EMG*

From the intramuscular EMG algorithm mentioned in section 2.3.2, the resultant matrices will be the variances for the pre-recording motor unit trains. The statistical model used will assess the difference between the pre- and post- recording motor units for each capsaicin and placebo as well as a between group comparison (Post-Pre capsaicin motor unit variance vs. Post-Pre placebo motor unit variance). These analyses would provide insight into our hypothesis that sensitization induced by capsaicin effects upon the motor unit characteristics. Either an independent samples t-test or a Kruskal-Wallis H test will be performed, depending on how many participants' pre and post motor units match up.

3 Sample Size Calculation

The minimum sample size required per group to detect whether a significant difference exists between two means for one dependent variable was calculated with a confidence level of 95%, a 80% statistical power level and 5% error. A mean detectable difference of 5 for the dependent variable, mean motor unit recruitment change, and an estimated standard deviation of 3 was used. The estimated sample size was 7 people per group; however, considering a 20% drop out rate, the suggested sample size was 9 people per group. This analysis was completed using PASS Software, version 15.

4 Conclusions

This may provide some insights for the neurophysiological influence of central sensitization on changes in efferent responses and movement patterns that occur in patients with persistent pain. However, the clinical implication of this experimental findings on the movement properties needs to be further investigated.

5 References

- [1] IASP, "Classification of chronic pain: descriptions of chronic pain syndromes and definitions of pain terms," *Pain* 1994; Suppl 3: 1–226.
- [2] I. o. Medicine, Relieving Pain in America: A Blueprint for Transforming Prevention, Care, Education, and Research, Washington,DC: The National Academies Press, 2011.

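### The 0.8–1.2 amplitude gate in section 2.3.1 is not reciprocal and its numerator is not stated, so an arbitrary coding choice decides whether some motor-unit pairs pass

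*Combined protocol and SAP*

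**What the plan says.** Section 2.3.1 (Amplitude Analysis) describes "calculating an amplitude ratio between pre- and post-recording motor units" and adds: "This amplitude ratio will be calculated for each pre/post motor unit pair". No formula names the numerator; pre/post there describes the pair, not a quotient. The gate follows: "amplitude ratios that are below a preset threshold of 0.8 or above 1.2 are set to 0". Eq. 1 then replaces the ratio by one minus the ratio "when the amplitude ratio is above one".

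The parallel shape gate has a stated purpose. Cross-correlations under 0.8 "will be set to 0 as the pair is unlikely to be from the same motor unit". The two scores are then combined: "The numbers from the shape analysis and amplitude analysis, which are not set to 0, will be averaged together". Algorithm 1 selects matches from the resulting matrix and ignores zeros. The matched pairs give each participant's mean change in recruitment order, and section 2.4.1 t-tests "post-pre capsaicin recruitment differences against post-pre placebo recruitment differences". No reason is given for the 0.8–1.2 limits, and there is no sensitivity analysis.

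**The concern.** If the limits of a ratio gate are reciprocals of each other, it does not matter which recording is on top. Here they are not, so it does, and the plan leaves the choice to whoever writes the code. Take a unit whose amplitude falls by 18%. Coded post/pre, its ratio is 0.82 and it passes. Coded pre/post, its ratio is 1/0.82 = 1.22 and it fails. Correcting Eq. 1 alone would not cure this, because the gate is a separate rule.

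Matching decides which units enter each participant's average, so the choice affects the composition of the analysed quantity. If unit amplitude moved in one arm only, it would also affect how many true pairs each arm loses.

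**Working it through.** **Inputs from the plan.** Gate 0.8–1.2, Eq. 1 and Algorithm 1 (section 2.3.1); planned difference 5 positions, SD 3, 80% power, 5% error, 20% dropout (section 3).

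**The plan's own figure.** A two-sided two-sample t-test with difference 5 and SD 3 has 74.0% power at 6 per group and 81.6% at 7. With dropout, 7/0.8 = 8.75, so 9. The stated 7 and 9 reproduce and are unaffected by this point; they supply the yardstick of 5 positions.

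**Step 1: asymmetry (no assumption needed).** ln 0.8 = −0.223 and ln 1.2 = +0.182. Expressed as post/pre:
- coded post/pre, the gate passes 0.80–1.20;
- coded pre/post, it passes 1/1.2 = 0.833 to 1/0.8 = 1.25.

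Pairs at 0.80–0.833 or 1.20–1.25 change status.

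**Step 2: share of true pairs affected.** Assume ln(post/pre) of true pairs is Normal(μ, s). The documents give neither value. With μ = 0, the share in the two bands is 2 × [Φ(−0.182/s) − Φ(−0.223/s)]. At s = 0.15 this is 2 × [Φ(−1.216) − Φ(−1.488)] = 2 × (0.112 − 0.068) = 8.7%. It is 4.3% at s = 0.10 and 9.7% at s = 0.20.

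**Step 3: pass rates by arm.** Pass rate = Φ((ln hi − μ)/s) − Φ((ln lo − μ)/s). With μ = 0 in both arms the two codings pass the same share (81.9% at s = 0.15), so the arm gap is zero either way. Now assume a 10% fall under capsaicin only, μ = ln 0.90 = −0.105. Gaps are in percentage points, computed before rounding.

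| s | Placebo, plan's gate | Capsaicin, post/pre | Capsaicin, pre/post | Gap, post/pre | Gap, pre/post | Gap, 0.8–1.25 gate |
|---|---|---|---|---|---|---|
| 0.10 | 95.3% | 87.9% | 77.9% | 7.4 | 17.4 | 9.4 |
| 0.15 | 81.9% | 75.6% | 68.2% | 6.3 | 13.8 | 9.4 |
| 0.20 | 68.7% | 64.7% | 60.0% | 4.0 | 8.7 | 6.4 |

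The last column is the reciprocal gate. It gives one answer whichever recording is on top, but the gap remains.

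**Step 4: what failing the gate means.** Step 3 treats a failing pair as lost. The averaging sentence can also be read as averaging only the non-zero parts, so that the pair survives on shape alone. That reading has an odd result: with shape 0.9, a pair at ratio 0.80 scores (0.9 + 0.8)/2 = 0.85, while one just below 0.80 scores 0.9. Simulating Algorithm 1 (assumed 20 units, log-amplitude SD 0.5, 15% of false pairs passing on shape), the numerator then moved the arm gap in true matches by only about 1 to 5 points.

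**Step 5: Eq. 1.** As written, a ratio of 1.00 scores 1.00, 1.01 scores −0.01 and 1.20 scores −0.20. With shape 0.9 the overall match drops from (0.9 + 1.00)/2 = 0.95 to (0.9 − 0.01)/2 = 0.445. The score leaves the intended 0–1 scale, and the numerator decides which pairs are marked down.

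**Step 6: effect on the endpoint.** A matching simulation assumed 20 of 28 units detected per recording, amplitude rising with recruitment order, a 2–10% false shape-pass rate, 1,500 participants per setting, and Eq. 1 read as 2 − ratio. A 10% fall under capsaicin produced a spurious shift of 0.11–0.33 positions (post/pre) or 0.14–0.46 (pre/post). The part due to the numerator is roughly 0.14 − 0.11 = 0.03 to 0.46 − 0.33 = 0.13 position, at most 0.13/5 = 2.6% of the planned difference.

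**The case against.** A band of 0.8–1.2 is a plain plus-or-minus 20% on the linear scale, so lack of log symmetry is not in itself an error. That is fair: the defect is the combination of a non-reciprocal band with an undefined ratio.

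The stronger objection concerns the arms. A reader might infer that the plan itself expects unit amplitude to fall under capsaicin, so that the coding choice biases the comparison. The Introduction does report, from a cited study, "A decrease in root mean squared (RMS) amplitude during exercise at the time of peak sensitization was measured by needle EMG". But that is the amplitude of a whole needle signal, which can fall because fewer units fire or they fire more slowly, with no change in any unit's amplitude. The gate acts on the average amplitude of each decomposed surface unit, and the Introduction goes on to say that effects on individual units had not been examined. The documents thus give neither a direction nor a size for the gated quantity, and the 10% fall is an illustration. This objection stands.

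Two further objections also stand. Unequal survival biases the mean only if survival is related to change in order or lets in false pairs. And the endpoint simulation replaces Eq. 1 with 2 − ratio, so it does not reproduce the plan exactly as written.

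**Conclusion.** The point holds as a minor specification defect. That the gate is not reciprocal and the numerator is undefined follows from the text alone. The share of true pairs changing status, about 4–10%, rests on an assumed normal log ratio with SD 0.10–0.20.

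A difference in match rates between arms is conditional on two things: an amplitude shift in one arm, and failing pairs being dropped. The documents establish neither. Even granting both, the numerator moves the mean recruitment change by about 0.1 position against the planned 5, under assumed simulation settings. An effect on the t-test's conclusion has not been shown. Nor should a reader infer that a reciprocal gate equalises the arms: at s = 0.15 with a 10% fall the gap is about 9 points, between the 6 and 14 of the two current codings.

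**What to change.** In section 2.3.1:
- define the amplitude score as min(pre, post)/max(pre, post), set to 0 when below 0.8;
- use it in place of Eq. 1;
- state that a pair failing either gate gets an overall match of 0;
- report the number and share of matched units by arm.

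The limit is then the same 1.25-fold change in both directions, the score lies within 0–1 by construction, and the numerator no longer matters.

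The cost is two or three sentences, one line of MATLAB and one descriptive row in the results. The downside is that the limit widens from 1.20-fold to 1.25-fold on one side and admits a few more candidate pairs. In the Step 6 simulation this kept about 0.4–0.6 more true matches per participant, with false matches essentially unchanged. The change does not remove a gap caused by a real amplitude shift, which is why match rates by arm are needed.

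Appendix A already reports assumption checks (p = 0.187 and 0.081). If matching code has been run, record the numerator it used and repeat the analysis with the new score as a sensitivity check.
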